4.2.3 Exploratory Endpoints

[REDACTED]

[REDACTED]

[REDACTED]

[REDACTED]

4.2.4 Safety Endpoints

The following are safety endpoints:

- Adverse Events (AEs)
- Clinical Laboratory Tests
- Vital Signs
- ECG
- Concomitant Medications

4.2.5 Pharmacokinetic Endpoints

The following are pharmacokinetic endpoints:

- Ganaxolone plasma concentration
- Maximum plasma concentration (C_{max})
- Time of maximum concentration (T_{max})
- Area under the concentration versus time curve from time 0 to t hours (AUC_{0-t})
- Area under the concentration versus time curve from time 0 to infinity (AUC_{inf})
- Clearance (CL). Calculated as dose/ AUC_{inf}

4.3 Planned Analyses and Analysis Population

Planned Analysis	Analysis Population			
	Screened Population	Safety Population	Pharmacokinetic Population	Comments
Subject Disposition	✓			
Demographic Characteristics		✓		
Baseline Characteristics		✓		
Prior and Concomitant Treatment		✓		
Protocol Violation		✓		
Efficacy Analyses		✓		
Safety Analyses		✓		
Pharmacokinetic Analyses			✓	

4.4 General Analysis and Reporting Convention

Since data from only open-label phase are analyzed, there will be only one treatment group. For efficacy and safety summaries, where applicable, subjects will be categorized into three cohorts (Cohort 1: High, Cohort 2: Medium, and Cohort 3: Low) based upon target dose of study medication. An overall group will also be reported representing all subjects.

General Convention:

The following are general conventions for the analysis of study data. If alternative methods are present in the specific evaluation sections of this SAP, those conventions will take precedence over these general conventions.

- Continuous study measurements will be summarized by treatment group (Open-Label Group or Cohorts and Open-Label Group) and time point (as applicable) using descriptive statistics (n, mean, standard deviation, median, minimum, and maximum). Means and medians will be presented with one more decimal place than the precision of the data. Standard deviations will be presented with two more decimal places than the precision of the data. Minimums and maximums will be presented with the same precision as the original data.

- Categorical study assessments will be summarized by treatment group (Open-Label Group or Cohorts and Open-Label Group) and time point (as applicable) using frequency counts and percentages. Unless stated otherwise, percentages are based on the number of subjects in the treatment group of the analysis set. Percentages will be presented with one decimal place (xx.x), with the exception of 100%, which will be displayed without any decimal places.
- Descriptive summaries based on the modified ITT (mITT) analysis set and per-protocol (PP) analysis set will be displayed by randomized treatment.
- Descriptive summaries based on the safety analysis set will be displayed by actual treatment received.
- All listings will be listed by cohort, subject, and time point (if applicable).
- Scheduled assessments will be included in summaries. Unscheduled assessments will only be included in the display sections that report abnormal laboratory, vitals, or ECG values. Data from all assessments (scheduled and unscheduled), will be included in listings.
- All statistical tests will be performed at a significance level of 0.05 (two-tailed). Where applicable, two-sided 95% confidence intervals will be reported. For tables.
- p-values will be reported to 3 decimal places, with values less than 0.001 displayed as '<0.001'. Unless otherwise noted, no adjustments for multiple comparisons will be made.
- No preliminary rounding will be performed; rounding should only occur after analysis. To round, consider the digit to the right of last significant digit: if <5 then round down, if ≥ 5 then round up.
- Unless stated otherwise, the baseline will be calculated as the last observed assessment (including scheduled and unscheduled assessments) before the initiation of dose. Change from baseline values will be calculated as the post-baseline value minus the respective baseline value.
- For the safety analysis set, prior medications are those that started and ended before the initiation of IV. Concomitant medications are those that started before initiation of IV and continued into blinded treatment or those that started after the initiation of IV of blinded treatment.
- Unless stated otherwise, available data from screen failures will be excluded from all tables and figures, but will be presented in any applicable data listings where data was collected for screen failure subjects.

Safety and Other Rules:

For adverse events with partially missing onset dates, an onset date is imputed as detailed in "Programming Specifications".

Missing or partially missing prior and/or concomitant start dates are imputed using the same rules for AE onset dates. If the stop date is missing the medication is considered to have been received during all periods after that determined by the start date (but see also rules for stop-date imputation).

Programming Specifications

a) All output should have the following header at the upper left margin:

Marinus Pharmaceuticals, Inc.
Study 1042-SE-2001

and the following header (right justified) at the upper right margin:

Page n of N
ddMMMyyyy

Tables/appendices/listings should be internally paginated (i.e., page numbers should appear sequentially within each table). All output should have SAS program name in the lower right, the data source(s) used to generate the output in the lower left.

b) In general, data listings should be sorted by cohort, subject number and time point/start dates, unless specific instructions to do otherwise.

c) The following algorithm should be used to estimate adverse event start dates and stop dates for which only partial information is known:

- When the year is present and the month and day are missing:
 - If the year is same as the year of first day on IV, then the day and month of the start date of IV will be assigned to the missing fields.
 - If the year is prior to the year of first day on IV, then December 31 will be assigned to the missing fields.
 - If the year is after the year of first day on drug, then January 1 will be assigned to the missing fields.
- When year and day are present and the month is missing:
 - If the year of AE start is same as the year of start of IV, then month will be set to the month of start of IV.
 - If the year is prior to the year of first day on IV, then month will be set to December.
 - If the year is after the year of first day on IV, then month will be set to January.
- When year and month are present and day is missing:
 - If the year of AE start is same as year of initiation of IV and:

- The month of AE start is same as month of initiation of IV, then the day will be set to the day of initiation of IV.
- The month of AE start is prior to the month of initiation of IV, then the day will be set to the last day of the month.
- The month of AE start is after the month of initiation of IV, then the day will be set to the 1st day of the month.
- If the year of AE start is earlier than the year of initiation of IV, then the day will be set to the last day of the month.
- If the year of AE start is after the year of initiation of IV, then the day will be set to the 1st day of the month.
- If the AE stop date is complete and the imputed start date as above is after the stop date, the start date will be set to AE stop date.
- Adverse events with partially missing stop dates will be imputed a stop date as follows:
 - *year is missing* - Date left missing.
 - *month is missing* - impute 'December'.
 - *day is missing* - impute 'last date of that month'.

d) Prior and Concomitant Medication Date: If the start date (or end date) of a medication is completely missing or only the day is known, then the start date (or end date) will not be imputed. Unless the end date is before the start date of IV, the medication is considered concomitant.

- For a partial start date of medication,
 - If the year is present and the month and day are missing, then the month and day will be set to January 1.
 - If the year and day are present and the month is missing, then the month will be set to January.
 - If the year and the month are present and the day is missing, then the day will be set to the 1st day of month.
 - If the imputed start date of medication is after the non-imputed end date of medication, then the start date will be set to the end date of medication.
- For a partial end date of medication,
 - If the year is present and the month and day are missing, then the month and day will be set to December 31.

- If the year and day are present and the month is missing, then the month will be set to December.
- If the year and the month are present and the day is missing, then the day will be set to the last day of month.

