#### **4.5.1 Subject Withdrawal Criteria**

All subjects reserve the right to withdraw from the clinical study at any time, as stated in the informed consent form. The investigator may also discontinue subjects from the clinical study for any of the following reasons:

1. The subject has persistent ventilatory depression that results in a SpO2 < 90% or ETCO2 > 50 mmHg (measured using nasal cannula monitor) despite the use of airway maneuvers including assisted ventilation. Standard airway maneuvers to treat sedation-induced upper airway obstruction (jaw thrust, chin lift, or supraglottic device such as a laryngeal mask airway) or hypoventilation (ventilation assisted with a mask or supraglottic device) would be instituted at the discretion of the physician monitoring the patient in order to maintain SpO2 > 90% and ETCO2 < 51 mmHg. If the subject does not respond to these methods, the subject would be discontinued
2. ECG evidence of QT prolongation (QTcF > 500 msec, or an increase of QTcF > 60 msec above baseline to a value > 480 msec on the 12-lead ECG, confirmed on a repeat 12-lead ECG taken after resting at least 5 minutes in a supine or semi recumbent position after the original finding of prolonged QTcF)
3. Kidney function impairment such that eGFR ≤ 45 mL/min and subject is not starting dialysis
4. Any other adverse event or safety issue (e.g., severe persistent hypotension/hypertension or tachycardia/bradycardia) that suggests it is not in the subject's best interest to continue to receive study drug
5. Rash that is clinically significant and considered to be related to the study drug (e.g., morbilliform, urticarial, papular)
6. Subject experiences an SAE considered to be related to the study drug

Decisions to discontinue the study will be made at each participating site by the principal investigator. If feasible, the reason for discontinuation should be discussed with the Medical Monitor prior to subject discontinuation unless due to the progression to an IV anesthetic drug (a 3rd line treatment) for seizure suppression.

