### 9.8 Safety Analyses

AEs will be coded using the Medical Dictionary for Regulatory Activities. The number of events, incidence, and percentage of treatment-emergent AEs will be calculated overall, by system organ class, by preferred term, and by treatment group. Treatment-emergent AEs will be further summarized by severity and relationship to study drug. AEs related to study drug, AEs leading to withdrawal, SAEs, and deaths will be similarly summarized and listed.

Clinical laboratory tests, vital signs, ECG findings, MRS, and FOUR Score will be summarized by treatment group and visit. Potentially clinically important findings will also be summarized or listed. Where applicable, the estimated subject mortality will be calculated using APACHE or APACHE 2 score.

The study team physician and the clinical operations lead will monitor emerging safety data from each subject periodically throughout the duration of the study. This data will be blinded for the double-blind group.

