4.9.5 Vital Signs

Vital signs are listed and summarized by time point and group (by cohort and overall) for the Safety Population. Systolic blood pressure, diastolic blood pressure, pulse, respiration rate, temperature, oxygen saturation, height, weight, and body mass index (BMI) will be summarized and listed. Both observed values and change from baseline will be summarized.

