4.9.6 Laboratory Evaluations

Laboratory findings will be listed and summarized for the Safety Population.

Chemistry, hematology, and urinalysis parameter results will be summarized using descriptive statistics by time point and group (by cohort and overall). Both actual values and change from baseline will be summarized. Similar table will be provided for AED laboratory results.

Summary showing number and percent of subjects with abnormal laboratory test results will be provided by time point and group (by cohort and overall) for hematology, chemistry, and urinalysis parameters.

Lab results, including AEDs, will be listed by cohort, subject, and time point.

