4.9.8 Electrocardiography

ECG measurements will be listed and summarized by time point and group (by cohort and overall) for the Safety Population. ECG parameters QT, QTcB, QTcF, PR, HR, and QRS will be presented. Summary of interpretation of ECG results will also be listed and summarized.

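### Unscheduled blood pressure and SpO2 values reach no vital-signs summary, and no worst-value or threshold table is planned for blood pressure, SpO2, QTcF or eGFR

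*SAP*

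**What the plan says.** The general convention in SAP 4.4 builds summaries from scheduled assessments. For the rest it says: "Unscheduled assessments will only be included in the display sections that report abnormal laboratory, vitals, or ECG values". It adds: "Data from all assessments (scheduled and unscheduled), will be included in listings". Continuous measures get "descriptive statistics (n, mean, standard deviation, median, minimum, and maximum" at each time point. A method given in a specific section overrides these conventions.

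The specific sections are short:

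- Vital signs (SAP 4.9.5): "Vital signs are listed and summarized by time point and group (by cohort and overall) for the Safety Population". Observed values and change from baseline are summarised.
- Laboratory (SAP 4.9.6): actual values and change by time point, plus "Summary showing number and percent of subjects with abnormal laboratory test results will be provided by time point and group". Chemistry is covered, and the schedule in SAP Appendix 1 places eGFR within serum chemistry.
- ECG (SAP 4.9.8): "ECG measurements will be listed and summarized by time point and group (by cohort and overall) for the Safety Population". QTcF is among the parameters, and the ECG interpretation is summarised too.

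Protocol 9.8 says: "Potentially clinically important findings will also be summarized or listed". Protocol 4.5.1 supplies numbers that could define such findings. One is "ECG evidence of QT prolongation (QTcF > 500 msec, or an increase of QTcF > 60 msec above baseline", with the increase counting only if the value exceeds 480 msec. Others are SpO2 below 90% and eGFR of 45 mL/min or less.

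**The concern.** Footnotes g, h and i of the SAP Appendix 1 schedule ask for extra vital signs, ECGs and laboratory samples when the investigator sees a clinically important change in the subject. Those readings are the likeliest to catch low blood pressure, desaturation or a long QTcF. Section 4.4 sends them to abnormal-value displays, and for vital signs no such display is specified. The same section lets an unscheduled reading serve as baseline, so unscheduled values may set the reference but may not enter the by-time-point summaries that are compared with it.

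Safety is part of the primary objective (SAP 2.1), and vital signs, ECGs and laboratory tests are named in a secondary endpoint (SAP 4.2.2). The open-label group exists partly for a preliminary look at safety before a separate phase 3 study, and it is reported in three dose cohorts. A reader comparing cohorts will want to know how many subjects in each had a low SpO2 or a long QTcF at any time. The planned tables do not answer that.

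**Working it through.** The documents state no figure on this point, so the check is mainly a tracing of each measure through the planned displays.

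**Step 1. Where an unscheduled value goes.**

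| Measure | Summary open to an unscheduled value | Worst-value or threshold table |
|---|---|---|
| Blood pressure, SpO2 | None in 4.9.5; listing only, or adverse event if judged significant | None |
| eGFR | Abnormal-chemistry count in 4.9.6, but laid out by time point with no stated row for it | None |
| QTcF | Interpretation summary in 4.9.8, if that counts as an abnormal display; the numeric value is left out | None |

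Sections 4.9.5 and 4.9.8 give no alternative rule, so 4.4 governs. Sections 4.9.5 and 4.9.6 both call for change from baseline; 4.9.8 does not. The increase of more than 60 msec in Protocol 4.5.1 is therefore not tabulated. That criterion also requires confirmation on a repeat ECG, which would usually be unscheduled.

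**Step 2. Protocol 9.8 against SAP 5.1.** The SAP contains no definition of potentially clinically important findings and no display with that purpose. SAP 5.1 records departures from Protocol 9.7.1, 9.7.2, 9.7.3, 9.9 and 9.9.1. It records none from 9.8.

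**Step 3. Illustration of how sparse the scheduled readings are.** The documents give no frequency, length or timing of excursions, so the following are assumptions: an excursion of length d hours lies wholly within the first 48 h, with a start time uniform on 0 to 48 − d. It overlaps a reading at time x if it starts between x − d and x. The share caught is the total length of those start windows, overlaps counted once and cut to the allowed range, divided by 48 − d. The reading at 48 h adds nothing, since such an excursion can touch it only at its end.

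- Vital signs, SAP Appendix 1 (nominal 2, 8, 24, 48 h). d = 0.5: 3 × 0.5 / 47.5 = 3%. d = 4: (2 + 4 + 4) / 44 = 23%.
- Vital signs, current protocol Table 1 (1, 2, 10, 24, 36, 48 h). d = 0.5: 5 × 0.5 / 47.5 = 5%. d = 4: (2 + 4 + 4 + 4) / 44 = 32%.
- ECG (2, 24, 48 h in the SAP; 2, 36, 48 h in the protocol). d = 0.5: 2 × 0.5 / 47.5 = 2%. d = 4: (2 + 4) / 44 = 14%, under either schedule.

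The 24 h and 48 h ECG times and the 48 h vital-signs time in the SAP schedule are nominal, since it asks only for one reading in each 24-hour period. The model does not suit eGFR, which does not move in short episodes, so none is given for it.

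**The case against.** The strongest reply is that extremes are not hidden. Minimum and maximum are shown at every scheduled time point. Abnormal chemistry is counted, and 4.4 expressly admits unscheduled values to abnormal-laboratory displays. ECG interpretation is summarised, and every reading is listed. Protocol 7.2.3.4 requires vital-sign deviations that the investigator judges clinically significant to be recorded as adverse events, and SAP 4.9.1 tabulates these by cohort. Protocol 9.8 allows findings to be listed rather than summarised. In a descriptive analysis of up to about 30 subjects, listings can be read one subject at a time.

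All of that is correct. A reader might infer from 4.4 that the worst blood pressure, SpO2, QTcF and eGFR values reach no summary at all; the documents do not support this, for the reasons just given. Nor do they show that Protocol 9.8 is broken outright, since full listings arguably meet its wording.

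The 4.5.1 criteria are also narrower than their numbers. They are grounds on which the investigator may discontinue a subject. The SpO2 limit applies to persistent depression despite airway support, QTcF needs a confirming ECG, and the eGFR limit applies only if dialysis is not being started. A single worst value cannot show that a criterion was met.

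The illustration has limits too. Uniform onset ignores that the bolus and highest infusion rate fall in the first 2 hours, when a reading is scheduled. A reader might infer that every excursion missed by the schedule sits in the unscheduled data, but whether anyone took a reading then is unknown.

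The gap in vital signs remains. The adverse-event route depends on judgement and counts no threshold crossings, and listings give no count by cohort.

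**Conclusion.** The point holds in a limited form. SAP 4.4 relies on an abnormal vital-signs display that 4.9.5 never specifies, so unscheduled blood pressure and SpO2 values reach no vital-signs summary. For laboratory results the placement of unscheduled values is undefined rather than excluded. For ECGs the numeric unscheduled QTcF is left out of the summaries, and neither outliers nor change from baseline are specified. No worst post-baseline or threshold table is planned for any of the four measures, and the SAP neither defines the findings named in Protocol 9.8 nor records the omission in 5.1.

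The size in subjects cannot be derived from the documents. The 2% to 32% in the illustration rests wholly on the assumed length and timing of excursions; it shows only that scheduled readings are sparse. The conclusion assumes that 4.4 is followed as written and that unscheduled readings are entered in the database, as the listing rule implies. The eGFR count is justified by the number in Protocol 4.5.1 alone: the documents cap daily Captisol but do not tie that cap to kidney function. This is an inexpensive improvement to a descriptive report, worth making before the tables are produced.

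**What to change.** Add one table to each of SAP 4.9.5, 4.9.6 and 4.9.8, by cohort and overall. Each gives the worst post-baseline value over all recorded readings, scheduled and unscheduled, from study drug initiation through the in-patient follow-up day (the SAP's 24-hour post-taper follow-up day).

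- 4.9.5: worst SpO2, with n (%) of subjects having any value below 90%. For blood pressure show the worst values only, lowest and highest, because 4.5.1 names both hypotension and hypertension but gives no numeric limit.
- 4.9.6: lowest eGFR, with n (%) having any value of 45 mL/min or less. State where unscheduled results enter the abnormal-laboratory table, for example in an added row for any post-baseline time.
- 4.9.8: highest QTcF and largest increase from baseline, with n (%) having any QTcF above 500 msec, or an increase above 60 msec to a value above 480 msec. Show separately those confirmed on a repeat ECG.

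Label the counts as values crossing the number, not as withdrawal criteria met. Record in SAP 5.1 how Protocol 9.8 is being handled.

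The cost is three tables from data already collected and listed, plus a few lines of text. The drawback is that sicker subjects are measured more often and so have more chances of an extreme value; report the number of readings per subject beside each table.

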## 8. ADVERSE AND SERIOUS ADVERSE EVENTS ASSESSMENT

### 8.1 Definition of Adverse Events, Period of Observation, Recording of Adverse Events

An AE is any untoward medical occurrence in a clinical investigation subject who has been administered a pharmaceutical product; it does not necessarily have a causal relationship with this treatment. An AE can therefore be any unfavorable and unintended sign (including an abnormal laboratory finding), symptom, or disease temporally associated with the use of a medicinal (investigational) product, whether or not related to the medicinal (investigational) product.

As this study allows for pre-consenting of subjects, all AEs will be collected from the time of first dose of study drug until the defined follow-up period stated in Section 7.1.3. Where possible, a diagnosis rather than a list of symptoms should be recorded. If a diagnosis has not been made, then each symptom should be listed individually. All AEs should be recorded on the appropriate AE pages in the eCRF and in source documents. In addition to untoward AEs, unexpected benefits outside the study drug indication should also be recorded on the AE eCRF page.

All AEs must be followed for the durations described below. For AEs followed to closure, this indicates that an outcome is reached, stabilization is achieved (the investigator does not expect any further improvement or worsening of the event), or the event is otherwise explained. When appropriate, medical tests and examinations are performed so that resolution of event(s) can be documented.

For subjects who:

- a. Have 2 days of treatment which includes a 12-hour study drug taper, all adverse events will be collected through the in-patient follow-up day. During the weekly follow-up visits only, ongoing AEs and new AEs assessed by the investigator to be related to study drug will be recorded. All SAEs regardless of relationship to study drug will be recorded from the time of 1st dose through the last follow-up visit/contact.

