4.9.1 Adverse Events

Adverse events are coded using the MedDRA dictionary, Version 20.1 or higher, and are categorized by system organ class (SOC) and preferred term (PT). Only treatment emergent adverse events are included in the summary tabulations. All adverse events are included in the data listings.

To allow differentiation as to which study period an Adverse Event occurred, two categories are defined based upon onset date. Adverse Events that had onset dates prior to the first dose of study medication are considered "prior". Adverse events with onset dates on or after the first dose of study medication and up to end of follow-up period are considered "on-therapy" or equivalently "treatment emergent". Adverse events with an onset date prior to the first dose of study medication but worsens after treatment starts are considered a treatment emergent AE.

Overall summary of Treatment-emergent adverse events (TEAE) will be provided. The TEAEs will be summarized by MedDRA System Organ Class (SOC) and preferred term (PT), and by group (by cohort and overall). Treatment-emergent adverse events will further be summarized by severity and relationship to treatment medication. Treatment-emergent Serious Adverse Events (SAE) and AEs leading to discontinuation of study drug will also be summarized by SOC, PT, and group (by cohort and overall).

Adverse events and serious adverse events will be listed.

Deaths will be listed and summarized by group (by cohort and overall).

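### The SAP's rule for an AE onset with a missing month can date a post-dose event before dosing and so leave it out of the TEAE tables

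*SAP*

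**What the plan says.** SAP 4.4, Programming Specifications item c, imputes partial AE dates. The relevant case is headed "When year and day are present and the month is missing". If the AE year equals the infusion year, "then month will be set to the month of start of IV"; the recorded day is kept. A separate branch covers the turn of the year: "If the year is after the year of first day on IV, then month will be set to January". One later adjustment applies to imputed starts when the stop date is complete: if "the imputed start date as above is after the stop date, the start date will be set to AE stop date".

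SAP 4.9.1 uses the resulting date to classify events. "Adverse Events that had onset dates prior to the first dose of study medication are considered" prior; those with onset on or after first dose are treatment emergent. It adds: "Only treatment emergent adverse events are included in the summary tabulations". All events, prior or not, appear in the listings.

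Protocol 8.1 sets the collection window: "all AEs will be collected from the time of first dose of study drug until the defined follow-up period" given in Section 7.1.3. Protocol 7.2.3.3 also starts collection at first dose.

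**The concern.** AE collection starts at first dose, so an event in this database should not have a pre-dose onset. A rule that creates one has most likely moved a genuine on-treatment event. The direction is anti-conservative: the event leaves the safety tables and nothing replaces it.

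The neighbouring branches avoid this. An event with only the infusion year known, or with the infusion year and month known, is placed on the infusion date and stays treatment emergent. For an event in the infusion year, the missing-month branch is the one that can turn a true post-dose onset into a pre-dose one.

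The open-label group is up to about 30 subjects (Protocol Synopsis), reported in three cohorts (SAP 1). If the cohorts were about 10 each (an assumption), losing one subject's only event of a given term would change that row by 1/10, or 10 percentage points.

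**Working it through.** The documents state no figure on this point, so there is none to reproduce. The check applies the rule as written.

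**Inputs**
- Rule: month set to the infusion month, day unchanged, when the years match (SAP 4.4 item c).
- Longest onset after dosing, Protocol Amendment 4: 48 h treatment including taper + 24 h in-patient day + (21 + 3) days = 27 days.
- Longest onset, SAP Appendix 1 schedule: 96 h + 18 h + 24 h = 138 h = 5.75 days; 5.75 + 24 = 29.75, about 30 days.
- Infusion dates: every day from 1 June 2018 to 31 May 2020, the planned study period in the Protocol Synopsis.

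**Algebra**
Let dosing be on day D of a month with L days, with onset k days later, in the next month. The recorded day is D + k − L. The imputed date has that day in the infusion month, so it precedes dosing when D + k − L < D, that is, when k < L. The shortest month has 28 days, so every k up to 27 meets the condition.

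**Examples**
- Dosed 28 March 2019, onset 3 April: imputed 3 March, 25 days before dosing.
- Dosed 5 March 2019, onset 1 April: imputed 1 March, before dosing.
- Dosed 28 December 2018, onset 3 January 2019: imputed 3 January 2019, correct.
- Dosed 10 February 2019, onset 11 March: imputed 11 February, wrong by a month but still treatment emergent.

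**Enumeration of all infusion and onset pairs**

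| Longest onset (days) | Onsets in a later calendar month | Of these, December to January (correct) | Same-year pairs | Same-year pairs dated before dosing |
|---|---|---|---|---|
| 24 | 7,200 | 600 | 6,600 | 6,600 (100%) |
| 27 | 9,072 | 756 | 8,316 | 8,316 (100%) |
| 28 | 9,744 | 812 | 8,932 | 8,904 (99.7%) |
| 30 | 11,156 | 930 | 10,226 | 9,844 (96.3%) |

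At 30 days the other 382 same-year pairs are 378 dated on or after dosing and 4 that give an impossible date, such as 30 February. No onset in the infusion month itself is misdated.

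**Share of missing-month records affected** (depends on an assumed onset distribution)
- Onset uniform over days 0 to 27: 8,316 / 20,468 = 0.41. Over days 0 to 24 it is 6,600 / 18,275 = 0.36, and over days 0 to 30 it is 9,844 / 22,661 = 0.43.
- Onset uniform over days 0 to 3, with a 30-day month: mean offset (0 + 1 + 2 + 3) / 4 = 1.5 days; 1.5 / 30 = 0.05. The December branch lowers this slightly, to 0.05 × 11/12 = 0.046.

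**Does another rule rescue the event?** The stop-date adjustment can only move a start earlier. The worsening clause keeps a pre-dose event that "but worsens after treatment starts are considered a treatment emergent AE", but Protocol 8.1.1 has a change in severity recorded as a new event, so the misdated record would still be prior.

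**The case against.** The strongest objection is practical. The trigger needs day and year known but month missing, which is an odd pattern. Early events arise in hospital, SAEs must be reported within 24 hours of awareness (Protocol 8.2.2), and entries are checked against source and queried (Protocol 9.1 and 9.2). No document gives a frequency, but very few such records should be expected. This stands.

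Uniform onset is also a poor description of the data. All AEs are collected only through the in-patient follow-up day. After that, new events are mainly those judged drug-related, SAEs and a short named list of complications (Protocol 8.1 and Synopsis). Recorded onsets should therefore cluster early, nearer the 5% figure. This stands too, although the later events that are recorded are ones a safety table should not lose.

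The event is not lost from the report. It stays in the listings, SAEs are listed, deaths are listed and summarised separately, and no formal inference is planned. This limits the consequence but does not make the tables right.

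A reader might go further and infer that any next-month event is misdated. The documents do not support that: the year branch handles December to January correctly, and an onset a full month length or more after dosing can stay on or after the dosing date.

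A reader might also infer that the stop-date rule, which sets a missing month to December, does the same harm. It does not. Treatment-emergent status does not use the stop date, SAP 4.9.1 plans no summary of AE duration, and unresolved events are followed to closure (Protocol 7.1.3 and 8.1), so a stop date beyond four weeks is not in itself an error.

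**Conclusion.** The rule is wrong as written in one branch: day and year known, month missing, AE year equal to the infusion year. Within that branch, a true onset in a later calendar month is dated before dosing in every case for onsets within 27 days, and in about 96% of cases at the SAP's longest schedule. Those percentages follow from the calendar and weight all infusion and onset days equally.

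The share of missing-month records affected is not known. It is about 5% if onsets fall within 3 days of dosing and about 40% if they are uniform over follow-up. Both are assumptions, and the collection rules point to the lower one. With few such records expected, the likely effect on the tables is small. It is worth correcting because the error is one-sided for safety and nearly free to remove.

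It is tempting to conclude that every imputed onset should be floored at first dose. The documents do not support that. Other branches use a recorded year or month that itself places the event before dosing, and the SAP deliberately keeps a prior category for such records.

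**What to change.** Change only the same-year, missing-month branch of SAP 4.4 item c:

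- Set the month to the earliest month in the recorded year that contains the recorded day and puts onset on or after the study drug start date.
- If no such month exists in that year (for example, dosed 20 December with day 5 of the same year), query the record. If it stays unresolved, set onset to the study drug start date.
- Leave unchanged the branches in which a recorded year or month places onset before dosing, and the branch for a later year.

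For onsets within 27 days of dosing in the recorded year, the new rule returns the true date, because the interval is shorter than any month. For longer onsets it may be out by a month, but the event stays treatment emergent.

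The cost is a sentence or two in the SAP and a small change to one branch of the imputation program. No new data are needed.
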